5.1.12.3 Respiratory system

In the event of abnormal spirometry results or persistent respiratory symptoms (e.g., dyspnea), the subject will be closely observed, spirometry will be repeated, and study treatment discontinuation should be considered, according to the guidance provided in Table 4.

15 March 2022, page 76/216

Confidential

Table 4 Guidance for subject monitoring and discontinuation for PFT decrease and persistent respiratory AEs

Item	Parameter	Guidance
1	If:	Repeat PFT within the next 2 weeks or
	>30% decrease from the study baseline	earlier if clinically indicated.
	FEV ₁ and/or FVC.	See item 1a, 1b.
1a	If at repeat PFT:	Discontinue study treatment and perform
	>30% decrease from the study baseline	FU PFTs.
	FEV ₁ and/or FVC and, in the	
	opinion of the investigator, this	
	change is clinically significant	
1b	If at repeat PFT:	Resume regular PFTs schedule.
	≤30% decrease from the study baseline	
	FEV ₁ and/or FVC	
	and	
	the subject does not have respiratory	
	symptoms (e.g., cough, dyspnea).	

Baseline = assessment done at Visit 2 (Baseline) of the core study; AE = adverse event; $FEV_1 =$ forced expiratory volume in 1 second; FU = follow-up; FVC = forced vital capacity; PFT = pulmonary function test.

If clinically significant, persistent respiratory AEs (e.g., dyspnea) are reported, PFTs must be performed and study treatment may be interrupted at the discretion of the investigator. In the event of study treatment interruption, the subject will be closely observed, FU PFTs will be performed, and further diagnostic work-up and consultation with a pulmonologist or other specialist should be considered according to local practice and the clinical situation. Following study treatment interruption, if PFTs normalize and lung toxicity is unlikely, study treatment may be re-initiated at the discretion of the investigator.

The decision to permanently discontinue study treatment will be made after evaluation of all available information concerning concomitant medication, other potential causes of respiratory AEs, and the clinical status of the subject. Further diagnostic work-up and consultation with a pulmonologist or other specialist should be considered according to local practice and the clinical situation.

Subjects experiencing respiratory symptoms and/or reduced pulmonary function during the course of the treatment with the study treatment may be prescribed short-acting $\beta 2$ agonist (to be used on an 'as needed' basis' use), at the investigator's discretion. If a subject fails to show symptom relief and/or reversibility, additional diagnostic work up (e.g., high-resolution computerized tomography, DLco) and/or permanent study treatment discontinuation should be considered at the discretion of the investigator.

Confidential

EudraCT 2016-004719-10 EDMS-ERI-207656619

In all cases of permanent discontinuation, FU monitoring must be provided until respiratory AEs have resolved and changes in pulmonary function are no longer regarded as clinically relevant, or until medically indicated.

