5.1.7 Accelerated elimination of teriflunomide and duration of continued contraception

Approximately half of the subjects in the core study received teriflunomide as their study treatment, but due to blinding, all subjects will undergo an accelerated elimination procedure followed by an assessment of compliance to the elimination procedure prior to administration of the first dose of ponesimod in the extension study.

During the early stages of the study (protocol versions 1 through 4), additional plasma teriflunomide tests may have been required to confirm that teriflunomide plasma levels were sufficiently low (<0.02 mg/L) before fertile male participants could stop contraceptive requirements and in the case of planned pregnancies (see Section 5.1.12.5). Following approval of

15 March 2022, page 67/216

Confidential

EudraCT 2016-004719-10 EDMS-ERI-207656619

protocol version 5, these tests are no longer required now that all ongoing subjects have been off teriflunomide for over 2 years (last subject entered this extension study on 20-May-2019) [Aubagio® USPI, Aubagio® SmPC].

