7.4.2 Detection and evaluation of relapses

Detection and evaluation of relapses will be done as follows [see Figure 3]:

Step 1: At every study visit, subjects are reminded to contact their principal investigator / treating neurologist immediately in the event of the appearance of any new or worsening neurological symptoms. In addition, the site will contact the subject 6 weeks (± 7 days) after each of the visits following Visit 4 (Week 12) in order to proactively inquire about any new or worsened neurological symptoms. If applicable, this may occur on site during blood sampling visits.

Whenever a subject experiences any new or worsening neurological symptoms between visits, he/she must contact the principal investigator / treating neurologist, study nurse or clinical coordinator as soon as possible in order to complete a telephone questionnaire for relapse assessment [see Appendix 10].

If, during the call from the site inquiring about symptoms suggestive of potential new relapses, the subject reports occurrence of such symptoms, a telephone questionnaire for relapse assessment will also be completed.

If a relapse is suspected, the subject will be required to come to the site for an unscheduled relapse assessment visit. The completed telephone questionnaire will be collected in the eCRF.

Step 2: At every visit (including unscheduled visits at which the subject is attended by the principal investigator / treating neurologist), the principal investigator / treating neurologist will interview and examine the subject to determine whether or not a relapse may have occurred since last visit using a dedicated relapse assessment questionnaire [see Appendix 10] and the relapse symptom form [see Appendix 11]. NB: Visits for laboratory re-test (due to a non-evaluable assessment, e.g., a non-analyzable blood sample, MRI rejected by MIAC for quality reasons), or repeated test (e.g., repeated test of serum leucocyte level or repeated PFT as required per protocol) are not considered scheduled or unscheduled visits. Unscheduled visits for safety reasons such as unscheduled ophthalmology assessments, unscheduled PFTs or unscheduled MRIs do not require relapse assessments unless in connection with or as a consequence of these assessment the subject is seen at the site by the principal investigator / treating neurologist.

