8.5.2 Unscheduled visits (any other assessment; U1, U2, U3, etc.)

An unscheduled site visit may be performed at any time during the study (between scheduled visits), as necessary, at the investigator's discretion. The date of the visit and the reason for such visits as well as any data related to study assessments performed at unscheduled visits will be recorded in the eCRF. During such visits, any of the following assessments may be performed at the investigator's discretion:

- EDSS/FS
- MS Relapse (if the subject is meeting the principal investigator / treating neurologist)
- MRI
- Assessment of concomitant medications
- Assessment of methods of contraception (for WOCBP only)
- Physical examination
- Dermatological examination
- Body temperature
- Body weight
- SBP/DBP

15 March 2022, page 121/216

Confidential

EudraCT 2016-004719-10 EDMS-ERI-207656619

- Teriflunomide plasma concentration[#]
- Pulse rate (to be assessed only if no 12-lead ECG is performed)
- Ophthalmological examination (e.g., presence of visual symptoms suggestive of active uveitis [see Section 5.1.12.7])
- OCT (e.g., presence of visual symptoms suggestive of macular edema or active uveitis [see Section 5.1.12.7])
- Complete laboratory tests including: hematology, blood chemistry, viral serology, urinalysis, urine or serum pregnancy test (for WOCBP only).
- IRT call return of study treatment bottles and unused medication, and dispensing of new bottles, if appropriate.
- Assessment of AEs and SAEs.

Important note: Teriflunomide testing is no longer required with the approval of protocol version 5

Additional unscheduled spirometry will have to be conducted in the event of respiratory symptoms (e.g., dyspnea) and in the event of FEV₁ or FVC at a scheduled visit showing decrease from extension study baseline by >30% during the course of the study. Administration of inhaled short-acting $\beta 2$ agonist (e.g., albuterol/salbutamol) for symptom relief may be performed at the discretion of the investigator. Administration of short-acting $\beta 2$ agonist will be collected in the eCRF.

If any of the laboratory variables listed in Section 7.5.12.2 need to be analyzed, this must be done at the central laboratory, except in case of emergency; if it has been done at a local laboratory, results must be recorded in the eCRF [see Section 7.5.12].

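### Table 4 row 1b sets its ≤30% limit on FEV1 and/or FVC rather than on both, so read literally a confirmed >30% fall in one measure can qualify for return to routine spirometry

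*Protocol*

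**What the plan says.** Protocol Section 5.1.12.3, Table 4, has three linked rows. Its footnote defines baseline as Visit 2 of the core study.

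- **Item 1.** A ">30% decrease from the study baseline" in FEV1 and/or FVC calls for a repeat test within two weeks, or sooner if clinically indicated, and refers to items 1a and 1b.
- **Item 1a.** If the repeat again shows a fall of more than 30% in FEV1 and/or FVC, and the investigator finds it clinically significant, study treatment is discontinued and follow-up tests are done.
- **Item 1b.** If the repeat shows "≤30% decrease from the study baseline" in FEV1 and/or FVC, and the subject has no respiratory symptoms, the instruction is "Resume regular PFTs schedule".

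No precedence between 1a and 1b is stated.

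Other text bears on the same situation:

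- The sentence introducing Table 4 says that after abnormal spirometry or persistent symptoms "the subject will be closely observed, spirometry will be repeated", and that discontinuation should be considered under the table's guidance.
- A later paragraph of the same section covers respiratory symptoms and/or reduced function treated with a short-acting β2 agonist: "If a subject fails to show symptom relief and/or reversibility", further work-up or permanent discontinuation should be considered at the investigator's discretion.
- Section 8.5.2 requires unscheduled spirometry for respiratory symptoms, and for FEV1 or FVC "at a scheduled visit showing decrease from extension study baseline by >30% during the course of the study".

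**The concern.** Items 1 and 1a use and/or correctly: one measure beyond the limit is enough. Row 1b reverses the inequality but keeps the same connective. The opposite of at least one measure being more than 30% down is both measures being at most 30% down. With and/or left in place, the measure that is within the limit satisfies row 1b even though the other is not.

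Table 4 holds the protocol's numeric lung-function stopping guidance, and bronchoconstriction is an adverse event of special interest (Appendix 4). Row 1b is also the only row that ends the extra testing. Exclusion criterion 3 (Section 4.3) bars entry for a fall of more than 30% from core baseline in either measure, which suggests that either is the intended safety threshold here too.

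**Working it through.** **Logic of the two rows.** Let F and V mean that FEV1 and FVC respectively are more than 30% below baseline at the repeat. Let S mean that the investigator judges the fall clinically significant, and Y that respiratory symptoms are present.

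- Row 1a = (F or V) and S.
- Row 1b as printed = (not F or not V) and not Y.
- Row 1b with both = (not F and not V) and not Y.

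F, V, S and Y give 2 × 2 × 2 × 2 = 16 combinations.

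| Outcome | Row 1b as printed | Row 1b with both |
|---|---|---|
| Meets 1b with one measure still >30% down | 4 | 0 |
| Of those, also meets 1a (opposite actions) | 2 | 0 |
| Meets neither 1a nor 1b | 6 | 8 |

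The 4 combinations are FEV1 alone or FVC alone more than 30% down, without symptoms, with the fall judged significant or not. The 2 conflicts are those judged significant. If both measures are more than 30% down, row 1b is not met under either wording.

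Under the corrected wording, the 8 combinations outside both rows are 6 with a fall of more than 30% judged not significant (with or without symptoms) and 2 with both measures within the limit but symptoms present. Six of the 8 are already outside both rows as printed. The correction adds 2: exactly one measure still down, not significant, no symptoms.

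**Interval if row 1b returns the subject to routine.** Scheduled on-treatment spirometry is at Week 4, at Weeks 48, 96, 144 and 192, and at end of treatment, planned for Week 240 (Table 1; Sections 8.3.3, 8.3.9 and 8.3.10).

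Section 5.1.7 states "last subject entered this extension study on 20-May-2019". From then to the Version 6 date of 15 March 2022 is 1030 days, and 1030 / 7 = 147.1 weeks. If the first dose came 7 days after entry, it is 146.1 weeks. Both exceed Week 144 plus its 14-day window (Week 146), so on schedule the visits up to Week 144 had passed. The remaining case is a Week 192 trigger with the repeat up to two weeks later:

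- Nominal dates: 240 − 192 − 2 = 46 weeks, to 240 − 192 = 48 weeks.
- With ±14 days at both visits: 238 − (194 + 2) = 42 weeks, to 242 − 190 = 52 weeks.

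The interval is shorter if end of treatment comes early or symptoms appear.

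**Does other text correct row 1b?** The introductory sentence refers to Table 4 for what follows, so it does not override the row. The β2-agonist paragraph leaves the next step to discretion and sets no repeat test. Section 8.5.2 measures from the extension baseline whereas Table 4 measures from the core baseline, so the two triggers are not the same. Section 8.5.2 also does not say what follows the repeat.

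**The case against.** The strongest reply is that and/or, carried down from item 1, means whichever measure or measures triggered the repeat. Row 1b would then mean that the triggering measure has recovered, and the usual single-measure case would give no conflict. This reading is natural, and it shows that the intent can be inferred. It does not remove the problem: overlap remains when both measures triggered and only one recovered, or when the second measure falls at the repeat. The table does not state this reading.

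It can also be said that Table 4 is titled as guidance, that permanent discontinuation is decided on all available information, and that an investigator who judges a fall significant would be expected to follow row 1a. All of that stands and limits the practical effect.

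Two stronger inferences are tempting, and the documents do not support them.

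- A reader might infer that a confirmed fall judged not significant is left without any monitoring unless a new rule is added. The introductory sentence and the β2-agonist paragraph already leave room for close observation, repeat testing and work-up. Making discontinuation depend on the investigator's judgement is the protocol's own choice.
- A reader might take Section 8.5.2 as the mandate for Table 4's first repeat, and then use the note in Section 7.4.2, that visits for a "repeated PFT as required per protocol) are not considered scheduled or unscheduled visits", to show that no further repeat can follow. The baselines differ, and that note concerns relapse assessment, so it cannot settle what a scheduled visit means in Section 8.5.2.

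**Conclusion.** The wording of row 1b is wrong as printed and worth correcting. For a symptom-free subject with exactly one of FEV1 and FVC still more than 30% below core baseline at the repeat, a literal reading gives return to routine. That contradicts row 1a if the fall is judged significant, and it sends a confirmed fall back to roughly annual testing if it is not.

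The practical effect is modest. The number of subjects affected is unknown, since the documents give no frequency. The 46 to 48 weeks (42 to 52 with visit windows) rests on a Week 192 trigger, treatment continuing to Week 240 and no symptoms. It is the ordinary scheduled gap, not a measured harm, and it applies only to subjects whom row 1b actually returns to routine.

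**What to change.** Reword row 1b so that it requires "≤30% decrease from the study baseline" in both FEV1 and FVC, together with the absence of respiratory symptoms. This removes both conflicting combinations and ensures that no subject with a measure still more than 30% down meets the return-to-routine row.

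Follow-up of a confirmed fall of more than 30% judged not clinically significant can stay under the existing close-observation and investigator-discretion text. An explicit further repeat test for these subjects is optional and for the sponsor to decide; if added, it needs a stated interval and a stopping point.

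The cost is a wording change to one row, by amendment or site clarification, with no new assessment type.

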5.1.12.4 Pregnancy

15 March 2022, page 77/216

If a subject becomes pregnant while on study drug, study treatment must be permanently discontinued. The investigator must counsel the subject and discuss the risks of continuing with the pregnancy and the possible effects on the fetus. All initial reports of pregnancy in female participants must be reported to the sponsor by the study site personnel within 24 hours of their knowledge of the event (see Section 10.3.1).

5.1.12.5 Planned pregnancy

Female subjects participating in the study and wishing to become pregnant during the study may stay in the study and will have the study treatment interrupted prior to pregnancy and re-started after delivery.

Before becoming pregnant the following protocol requirements must be met:

- The wish to become pregnant and stay in the study must be communicated by the female subject to the principal investigator / treating neurologist during a scheduled visit.
- Prior to interrupting contraception, the subject must have 2 negative urine pregnancy tests: one
 at the scheduled visit on the day of study treatment interruption and one 30 days after study
 treatment interruption.
- The total duration of the study treatment interruption due to planned pregnancy must not exceed 81 weeks, otherwise the study treatment will be discontinued.
- The interruption of contraception must take place after Visit 5 (Week 24) and at earliest 6 weeks after the first of two consecutive tests confirming plasma teriflunomide level <0.02 mg/L[#] and at least 30 days after ponesimod interruption.
- The subject must agree to be followed by an appropriate health care professional (e.g., gynecologist, obstetrician and/or midwife) during pregnancy according to local practice, to have the reports from pregnancy assessments communicated to the principal investigator / treating neurologist and to have the information on the subject's MS status communicated by the principal investigator / treating neurologist to that health care professional.

Important note: Teriflunomide testing is no longer required with the approval of protocol version 5

15 March 2022, page 78/216

Confidential

EudraCT 2016-004719-10 EDMS-ERI-207656619

In addition to the protocol requirements above, the principal investigator / treating neurologist must explain the following to the subject:

- The potential impact of pregnancy and the post-partum period on the subject's MS and potential medical treatments that would be available for the subject while the study treatment is interrupted.
- Re-initiation of study treatment can only take place after delivery and breastfeeding has ended, if applicable, and will require a medical evaluation of subject's eligibility for study treatment re-initiation.
- Timing of the interruption and possible re-initiation of study treatment and of contraception, related urine pregnancy tests and unscheduled visits.
- The need for re-uptitration at the study treatment re-initiation.
- Breastfeeding must be completely stopped prior to the re-initiation of the study treatment.
- The need to follow the visit schedule as per protocol during pregnancy, including all scheduled assessments and procedures except MRI, PFTs, and without study treatment dispensing.

The re-start of study treatment after delivery requires the following eligibility criteria to be met:

- The subject has completely stopped breastfeeding prior to re-start of the study treatment.
- The subject must have been using the reliable methods of contraception as described in Section 4.4.1 for at least 30 days prior to re-start of study treatment.
- The subject must have had 2 negative urine pregnancy tests performed 30 days apart; the second one must be during the re-start visit.
- The subject did/does not fulfill any protocol criteria for permanent study treatment discontinuation [see Section 5.1.12] at any of the previous visits or at the unscheduled visit for re-start of the study treatment, except the planned pregnancy.
- If the subject received another DMT (IFN β or glatiramer acetate) during pregnancy and post-partum, this treatment must be discontinued at least 7 days before study treatment re-start.

If the subject agrees to all of the above, the study treatment will be interrupted at the scheduled visit once the subject, after having received the above explanation from the principal investigator / treating neurologist, has confirmed the wish to become pregnant and interrupt and potentially restart the study treatment. The sponsor must be contacted in each particular case in order to confirm that the subject who wishes to become pregnant can continue in the study.

The above requirements for re-initiation of study drug after delivery apply to all cases of study treatment interruption for planned pregnancy irrespective of the duration of pregnancy, and also

EudraCT 2016-004719-10 EDMS-ERI-207656619

Confidential

to all cases where planned pregnancy did not occur but where contraception was interrupted for any duration, and the subject thereafter wishes to re-start study treatment.

5.1.12.6 Liver abnormalities

15 March 2022, page 79/216

In the event of abnormal liver tests or signs and symptoms suggestive of drug-induced liver injury (DILI), the subject will be closely observed, liver tests will be repeated, and study treatment discontinuation should be considered according to the guidance provided in Table 5.

Note: All events of ALT or AST $\ge 3x$ ULN and total bilirubin $\ge 2x$ ULN ($\ge 35\%$ direct bilirubin) or ALT or AST $\ge 3x$ ULN and INR ≥ 1.5 may indicate severe liver injury (possible 'Hy's Law') and must be reported to sponsor in an expedited manner and as an SAE if SAE criteria are met. The INR stated threshold value will not apply to participants receiving anticoagulants.

15 March 2022, page 80/216

Confidential

Table 5 Guidance for subject monitoring and discontinuation for liver enzyme abnormalities

Item	Laboratory parameter	Guidance
1	ALT or AST ≥3 × ULN *	Start close observation. Repeat labs within 72 hours. See items 1a and 1b. * if ALT or AST ≥8 × ULN OR ALT or AST ≥3 × ULN and TBL ≥2 × ULN or INR >1.5a OR ALT or AST ≥3 × ULN with the appearance of fatigue, nausea, vomiting, right upper quadrant pain or tenderness, fever, rash, and/or eosinophilia (>5%) and retest cannot be done within 72 hours, permanently discontinue study treatment, and perform FU
1a	If at repeated labs, ALT or AST ≥3 × ULN < 8 × ULN	Continue close observation. Repeat labs twice weekly. See items 2a and 2b.
1b	If at repeated labs, ALT or AST <3 × ULN	Resume regular labs schedule.
2a	If at repeated labs, ALT or AST \geq 5 × ULN for >2 weeks	Permanently discontinue study treatment, and perform FU.
2b	If at repeated labs, ALT or AST ≥3 × ULN <5 × ULN for >2 weeks	Continue close observation. Repeat labs once or twice weekly.
3	 If at repeated labs: ALT or AST ≥8 × ULN ALT or AST ≥3 × ULN and TBL ≥2 × ULN or INR >1.5 a ALT or AST ≥3 × ULN with the appearance of fatigue, nausea, vomiting, right upper quadrant pain or tenderness, fever, rash, and/or eosinophilia (>5%) 	Permanently discontinue study treatment, and perform FU.

ALT = alanine aminotransferase; AST = aspartate aminotransferase; FU = follow-up; INR = International Normalized Ratio; TBL = total bilirubin; ULN = upper limit of normal range.

a Note: All events of ALT or AST ≥3xULN and total bilirubin ≥2xULN (>35% direct bilirubin) or ALT or AST ≥3xULN and INR >1.5 may indicate severe liver injury (possible 'Hy's Law') and must be reported to sponsor in an expedited manner and as an SAE if SAE criteria are met. The INR stated threshold value will not apply to participants receiving anticoagulants.

15 March 2022, page 81/216

Confidential

EudraCT 2016-004719-10 EDMS-ERI-207656619

Whenever AST or ALT $\geq 3 \times 10^{-5}$ the upper limit of normal range (ULN) are recorded by the central laboratory, an alert will be sent to the principal investigator and the sponsor. The sponsor will contact the principal investigator to ensure that she/he will immediately contact the subject, and ask the subject about any potential symptoms. The subject will be closely observed and will be asked to return to the site as soon as possible after the time of receipt of the alert to repeat the liver enzyme and bilirubin tests by the central laboratory (unless the clinical situation mandates immediate local testing) according to the scheme illustrated in Table 5. Further diagnostic work-up (including hepatitis serological testing by the central lab) and consultation with a hepatologist or other specialist should be considered, and adequate medical management should be provided according to local practice and the clinical situation. Any clinically relevant finding meeting the definition of an AE will be recorded accordingly in the eCRF.

In the event of study treatment interruption, the subject will be closely observed and FU liver tests will be performed. Following study treatment interruption, if liver tests normalize and drug-related hepatotoxicity is unlikely, study treatment may be re-initiated at the discretion of the investigator. The decision to permanently discontinue study treatment will be made after evaluation of all available information concerning concomitant medications, other potential causes of hepatotoxicity, and the clinical status of the subject. NB: The re-initiation is not permitted for situations where the study treatment should be permanently discontinued according to Table 5. In all cases of permanent study treatment discontinuation, FU monitoring must be provided until signs and symptoms have resolved and changes in liver function are no longer regarded as clinically relevant or until medically indicated.

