1.3.2.4 Safety and tolerability

Clinical studies to date have identified transient changes in heart rate (HR) and atrioventricular (AV) conduction as the most prominent safety-related signal with ponesimod. Oral doses of ponesimod resulted in dose-dependent sinus rate reductions in all treated subjects; the changes were transient and resolved largely within 6–10 hours after dosing. In some subjects, these HR reductions were accompanied by a transient effect on AV conduction with prolongation of the PR interval on the electrocardiogram (ECG) and, occasionally, second degree AV-block. The effects on HR and AV conduction diminish with repeated administration of ponesimod, indicating

15 March 2022, page 47/216

EudraCT 2016-004719-10 EDMS-ERI-207656619

Confidential

desensitization. To minimize the first-dose effects on HR and AV conduction, a dose up-titration regimen was successfully tested and has been implemented in current clinical trials.

Difficulty in inspiration (dyspnea) and related pulmonary function test (PFT) changes have also been detected in humans. Mild transient dyspnea/cough was noted frequently 2–6 hours after an oral dose of 40 mg or higher, and was associated with a clinically relevant forced expiratory volume in 1 second (FEV₁) decrease from baseline. Symptoms resolved spontaneously upon discontinuation of treatment with ponesimod, and PFTs returned to baseline upon drug discontinuation.

Elevations of aspartate transaminase (AST) and/or alanine aminotransferase (ALT) without any bilirubin increase have been noted with ponesimod; they have been reversible upon discontinuation of dosing. The changes were asymptomatic.

Individual cases of macular edema associated with changes in visual acuity have been observed in subjects treated with ponesimod. These events resolved upon discontinuation of ponesimod.

Safety results from the completed OPTIMUM study and the interim analysis of the ongoing AC-058B201/B202 study were consistent with previous studies and provide support for the long-term safety of ponesimod. Results of the AC-058B301/OPTIMUM study also support the safety and tolerability of the gradual ponesimod up-titration regimen.

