- In the OPTIMUM study, the proportion of subjects who experienced at least one TEAE was similar in both treatment arms (88.8% and 88.2% of subjects in the ponesimod 20 mg and the teriflunomide 14 mg arms, respectively). The most common TEAEs in the ponesimod 20 mg arm were ALT increased (19.5%), nasopharyngitis (19.3%), headache (11.5%) and upper respiratory tract infections (10.6%). Initiation of ponesimod using the gradual uptitration regimen (starting with ponesimod 2 mg) was not associated with clinically significant bradyarrhythmia events; none of the reported bradyarrhythmia events was serious or leading to discontinuation of treatment; no second- or higher degree AV blocks were reported.
- In the interim analysis of AC-058B201/B202 (cut-off date of 31 March 2019), long-term treatment with ponesimod was not associated with new safety or tolerability concerns. Study AC-058B202 is ongoing. The results of the interim analysis support the long-term benefit/risk profile of the 20 mg dose as the most optimal dose of ponesimod. Ponesimod 20 mg was shown to be safe and well tolerated in adults with RRMS over long-term treatment of up to 9 years (median exposure to ponesimod in the 20 mg dose group of 8.02 years, corresponding to a total of 817 subject-years).

15 March 2022, page 48/216

EudraCT 2016-004719-10 EDMS-ERI-207656619

Confidential

Nonclinical safety testing of ponesimod indicates an embryotoxic and teratogenic potential. Pregnant or lactating women are excluded from clinical trials, and women of childbearing potential (WOCBP) must use reliable methods of contraception and must not become pregnant during exposure to the study treatment and for at least 30 days after study treatment discontinuation. A hormonal contraceptive is allowed as one of the required methods of contraception, as the PK profile of hormonal contraceptives has been shown not to be substantially altered in the presence of ponesimod.

More detailed information can be found in the IB [Ponesimod IB].

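### Table 5 item 1b ends close liver monitoring when only one of ALT and AST is below 3 × ULN, even if the other is still at or above 3 × ULN

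*Protocol*

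**What the plan says.** Table 5 in section 5.1.12.6 sets out what to do when liver enzymes rise.

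- **Item 1** applies when ALT or AST is ≥3 × ULN. Its basic action is "Start close observation. Repeat labs within 72 hours. See items 1a and 1b".
- **Item 1a**: "If at repeated labs, ALT or AST ≥3 × ULN < 8 × ULN". Action: "Continue close observation. Repeat labs twice weekly".
- **Item 1b**: "If at repeated labs, ALT or AST <3 × ULN". Action: "Resume regular labs schedule".
- **Item 2a**: either enzyme ≥5 × ULN for more than 2 weeks. Action: permanent discontinuation and follow-up.
- **Item 2b**: either enzyme from 3 to <5 × ULN for more than 2 weeks. Action: continued close observation with labs once or twice weekly.
- **Item 3**: either enzyme ≥8 × ULN, or ≥3 × ULN with a bilirubin, INR or symptom/eosinophilia criterion. Action: permanent discontinuation and follow-up.

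The text after the table applies whenever the central laboratory records AST or ALT ≥3 × ULN. It requires an alert and states "The subject will be closely observed and will be asked to return to the site as soon as possible", with retesting to follow the Table 5 scheme.

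**The concern.** In every other row, *ALT or AST* at or above a threshold means that either enzyme is enough. That is right for a trigger. The way out of a trigger is its negation, and the negation of *ALT or AST ≥3 × ULN* is *ALT and AST both <3 × ULN*. Item 1b keeps the *or*, so one enzyme below 3 × ULN satisfies it.

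Item 1b is the only row that releases a subject from close monitoring. Chemistry is scheduled every 4 weeks only for the first 24 weeks (Table 1, note 9) and with the 12-weekly visits after that. The last subject entered on 20 May 2019 (section 5.1.7) and this version is dated 15 March 2022, so every ongoing subject is past Week 24. For them the regular schedule can mean about 12 weeks to the next chemistry test, against two tests a week under item 1a. Release would also end the repeat tests that item 2a needs to establish ≥5 × ULN for more than 2 weeks.

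A rise in one enzyme alone is foreseen. Section 1.3.2.4 states: "Elevations of aspartate transaminase (AST) and/or alanine aminotransferase (ALT) without any bilirubin increase have been noted with ponesimod". The same section lists ALT increased first among the most common treatment-emergent events on ponesimod 20 mg in the core study, at 19.5%. That is not a rate of ≥3 × ULN, nor of ALT and AST diverging, and it says nothing about how often item 1b would misfire.

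**Working it through.** The plan gives no figure to reproduce; the check is one of rule logic.

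**Inputs.** The conditions and actions of items 1a, 1b, 2a, 2b and 3 as worded, with *or* read literally. The table's own cut-points give four bands per enzyme: <3, 3 to <5, 5 to <8 and ≥8 × ULN. Hence 4 × 4 = 16 ordered ALT/AST pairs.

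**Pairs that meet item 1b.**

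- Both enzymes <3 × ULN: 1 × 1 = 1 pair. Release is correct.
- Exactly one enzyme <3 × ULN: 2 × 1 × 3 = 6 pairs. Release is literally allowed while the other enzyme is ≥3 × ULN.
- Neither enzyme <3 × ULN: 3 × 3 = 9 pairs. Item 1b is not met.

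Check: 1 + 6 + 9 = 16.

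**What the other rows require for those 6 pairs.** Each band of the raised enzyme accounts for 2 pairs.

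| Raised enzyme | Plain retest | Raised for >2 weeks, no further criterion | Bilirubin, INR or symptom criterion present |
|---|---|---|---|
| 3 to <5 × ULN (2 pairs) | 1a: twice-weekly labs | 1a and 2b: observe | 3: stop |
| 5 to <8 × ULN (2 pairs) | 1a: twice-weekly labs | 2a: stop | 3: stop |
| ≥8 × ULN (2 pairs) | 3: stop | 2a and 3: stop | 3: stop |
| **Opposed to item 1b** | **4 observe, 2 stop** | **2 observe, 4 stop** | **6 stop** |

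**Single cases.** ALT 6 × ULN with AST 2 × ULN: 3 ≤ 6 < 8, so item 1a holds; 2 < 3, so item 1b holds. ALT 9 × ULN with AST 2 × ULN: 9 ≥ 8, so item 3 holds; 2 < 3, so item 1b holds.

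**A finer grid.** Values of 1, 2.9, 3, 4.9, 5, 7.9, 8 and 10 × ULN for each enzyme give 64 pairs. Of these, 16 meet items 1a and 1b, 16 meet item 1b with an enzyme at the item 2a level (≥5 × ULN), and 8 meet item 1b with an enzyme ≥8 × ULN. The groups overlap and the counts depend on the grid; the existence of the conflict does not.

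**With item 1b reworded to both enzymes <3 × ULN.** Only the single pair with both <3 × ULN meets it, and that pair meets no other row. Conflicts fall to 0 of 16 in every setting, and to 0 of 64 on the finer grid. No pair is left without a row.

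Overlap between the observation rows (1a, 2b) and the stop rows (2a, 3) is not counted as a conflict, since a subject can be observed closely and stopped.

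**The case against.** The strongest reply is that the intent is plain. Item 1 points to items 1a and 1b together, so they read as the two outcomes of one retest: still raised, or no longer raised. Most investigators would take item 1b to mean both enzymes. There are also backstops. The text after the table applies whenever either enzyme is ≥3 × ULN, not only the first time, and Table 11 in Appendix 5 sets alerts for ALT and AST separately at ≥3, ≥5 and ≥8 × ULN. A divergent retest at the central laboratory would trigger the alert again. Item 1b concerns only the laboratory schedule: it does not cancel a stop rule, and section 5.1.12.6 bars re-initiation where Table 5 requires permanent discontinuation. Finally, the counts are cells in a grid, not patients.

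Much of this stands, and it limits the practical risk. It does not make the row right. The alert sends the investigator back to Table 5 and so to the same two rows. Nothing in the table, its footnote or the surrounding text says that item 1b needs both enzymes, or that another row prevails. For the stop rows, item 1b indeed leaves the stop in force. The clash remains, because a permanently discontinued subject moves to follow-up monitoring and the end-of-treatment and end-of-study visits, not back to the regular labs schedule.

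**Conclusion.** The concern holds: item 1b is wrong as written. With *or* read literally, it releases a subject with one enzyme <3 × ULN whatever the other shows, against items 1a, 2a, 2b and 3 and the text that follows the table. Six of 16 band combinations carry opposing instructions; in 2 to 6 of those 6, depending on the setting, the opposing row is a permanent stop. These counts rest on the table's own cut-points and describe possible results only; the protocol gives no basis for a patient frequency.

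The point should be corrected, but the likely harm is modest given the evident intent and the separate central-laboratory alerts. No efficacy analysis is affected. It does not depend on the SAP, because this is a subject-management rule that the protocol itself fixes.

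**What to change.** Reword the condition of item 1b to require that ALT **and** AST are **both** <3 × ULN at the repeat test. That alone removes every opposing instruction.

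Two optional clarifications: key items 1a and 2b to the higher of the two enzymes, and state that the stop rows (2a and 3) govern when more than one row is met.

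No threshold, test, visit or action changes. The text change is a few words in one table row, but section 13.6 requires a written amendment for any protocol change, and the study runs at about 160 sites in 28 countries. The sensible course is to bundle the correction with the next amendment.
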